9.5. Statistical test method

The test does not include the classification of unknown/not provided. In principle, the first layer is subjected to the intersegmental test of classified data. Multiplicity is not adjusted.

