9.6. Significant level

In principle, the significant level is 5%, two-tailed. $p < 0.05$ ($< 5\%$) shall be considered significant.

10. Derivation and calculation methods for data

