	
record - 1 day for the final administration date.
 
Of note, if the final administration date is provided in the record where the final administration date of Humira has been identified according to the above rule and the “continued” checkbox is checked, follow the below:
 
 ● If the described final administration date > the final administration date imputed according to the above rule, select the imputed final administration date as the final administration date of Humira for the patient. ● If the described final administration date <= the final administration date imputed according to the above rule, select the described final administration date as the final administration date of Humira for the patient. 
If the first administration date of Humira + 1092 days < the final administration date of Humira imputed according to the above rule, select the first administration date of Humira + 1092 days as the final administration date of Humira.

Days to the final administration date of Humira	The final administration date of Humira - the first administration date of Humira + 1
Total exposure period (in years)	(Days to the final administration date of Humira + 28) / 364
Discontinued patients	
 • Patients whose final administration date of Humira comes before the first administration date of Humira + 1064 (Week 152) • Patients with a washout period with 60 days or longer. 
*The final administration date of Humira should be the administration date right before the washout of ≥ 60 days starts.

Reason for discontinuation	When a reason for discontinuation is described in the survey form, it is defined as ‘with’ reason for discontinuation. When no such description is found, it is defined as an “unknown/not provided”.
Death cases	At least a piece of data on “death” is found as the outcome of the adverse events during the safety analysis period.
Pediatrics	Patients aged < 15 years
The elderly	Patients aged ≥ 65 years

Data name	Derivation and calculation methods
Presence/absence of complications	When complication data are contained in the survey form, it should be classified as “with complications”. When the description in the survey form is not clear enough (when the check of with/without complications is not assessable or when multiple checkboxes are checked), it should be ‘unknown’ while no description should be ‘not provided’. Other cases are “no complications”.

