Days from the first administration date of Humira to the adverse-event onset date	
Use the onset date for company assessment provided in “Humira CD long-term_AE matching list”.
 
When the first administration date of Humira and the adverse-event onset date can be identified as the complete date, they can be used for calculation.
 
When the first administration date of Humira <= the adverse-event onset date:
 
Adverse-event onset date - the first administration date of Humira + 1
 
When the first administration date of Humira > the adverse-event onset date:
 
Adverse-event onset date - the first administration date of Humira
 
When more than one identical PT is found in a patient, use the first onset date to identify the adverse event to be counted.

Days from the adverse-event onset date to the outcome confirmation date (recovered or recovering)	
Use the onset date and the outcomes (recovered or recovering) for company assessment provided in “Humira CD Long_AE matching list”.
 
When the adverse-event onset date and the outcome confirmation date can be identified as the complete date, they can be used for calculation.
 
Outcome confirmation date - adverse-event onset date + 1
 
When more than one identical PT is found in a patient, choose the event which persisted longest until the recovery or the outcome confirmation date.

Data name	Derivation and calculation methods
Incidence of adverse reactions, incidence of serious adverse reactions, incidence of adverse events, incidence of serious adverse events	
Calculate the incidence of adverse reactions, incidence of serious adverse reactions, incidence of adverse events, incidence of serious adverse events with the number of patients with any of the reactions/events in numerator and the number of patients in the safety analysis group in denominator.
 
Provide how to calculate in each table at Chapter 13 and thereafter if other calculation methods are used.

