Calculate the number of patients and the percentage to the number of patients surveyed per number of patients surveyed, number of patients with adverse reactions, etc. number of adverse reactions, type of adverse reactions, etc. (SOC, PT).

Note: Aggregate the initial reactions among the identical PTs in a patient. Aggregate the events based on the segments which contain the initial onset period of adverse reactions among Time Allowance defined in “12.4 Assessment period for the onset status of adverse reactions”. When calculating the number of patients with the target reactions, remove overlapped data per case number and onset period. When calculating the number of SOC, remove the overlapped data per case number, onset period and SOC.

Count the number of target patients and reactions by using the dates defined below until the assessment period applicable to Time Allowance defined in “12.4 Assessment period for the onset status of adverse reactions”.

- Discontinued patients: the final administration date of Humira + 28 days
- Not discontinued patients: the first administration date of Humira + 1120 days

Even if there is one adverse reaction, it should be counted as one patient in every period when the reaction persisted.

“2.9 Incidence of adverse reactions (serious adverse reactions/adverse reactions) per background factor”

Patients for analysis: patients in the safety analysis group

Analysis objective: to show the incidence of adverse reactions per patient background factor and analyze them.

Analysis items: calculate the number of all patients, the percentage to the number of patients with serious adverse reactions and all patients, the number of patients with adverse reactions and the percentage to number of all patients, the tests for adverse reactions (Fisher's exact test for nominal-scale factors and Man-Whitney's u test for ordinal-scale factors) per the following patient background factor regarding the adverse reactions which occurred in the safety analysis period. Note that the test does not include the patients "with treatment history with anti-TNF α drug for Crohn's disease".

Note: the patient background factors are as follows:

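### Chart 2.9 tests crude reaction percentages across background factors although observation ends when Humira stops, so levels tied to earlier stopping look safer than they are

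*SAP*

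**What the plan says.** The stated aim of chart 2.9 (SAP 13.2) is "to show the incidence of adverse reactions per patient background factor and analyze them". For each level of each background factor, it reports "the number of patients with adverse reactions and the percentage to number of all patients". It tests that yes/no outcome with "Fisher's exact test for nominal-scale factors and Man-Whitney's u test for ordinal-scale factors". This follows the general incidence definition in SAP 10.2, which works "with the number of patients with any of the reactions/events in numerator and the number of patients in the safety analysis group in denominator". SAP 9.6 sets the level ("In principle, the significant level is 5%, two-tailed") and SAP 9.5 adds "Multiplicity is not adjusted". Chart 2.9.xx then produces detailed tables only for the factors found significant in 2.9.

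Four other provisions matter.

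- **End of observation.** Protocol 8(1) treats suspension of Humira for at least 2 months as discontinuation of treatment, and that as discontinuation of the survey. Protocol 6(3) item 4 has the CRF completed when treatment stops.
- **Event window.** SAP section 2 counts events up to Day 1 + 1120 for every patient, stopped or not, and includes undated events.
- **Time at risk elsewhere.** Charts 2.6 and 2.7 end counting at last dose + 28 days for discontinued patients and at Day 1 + 1120 for the others. Chart 2.4.2 gives events per 100 patient-years, but only for the priority survey items and not by factor.
- **Exposure.** SAP 10.1 already derives exposure in years, from "Days to the final administration date of Humira + 28) / 364".

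**The concern.** A patient watched for three years has more opportunity to show a first reaction than one watched for three months. If a background factor is associated with how long patients stay on Humira, the crude percentages differ between its levels even when the reaction rate per year is the same.

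The bias has one direction. The level with earlier stopping looks safer, and the level with longer treatment looks riskier. It can produce a significant factor where none exists, or cancel a real excess in the patients who stop early. For a survey that lists factors affecting safety among its analysis items (Protocol 9(1), SAP 5.1), the second error is the more serious. Because the 2.9 p-values choose the factors for 2.9.xx, the bias also shapes which results are shown in detail.

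**Working it through.** **The plan's own figure.** Patients needed to see at least one malignant tumour with probability 95% at 1.0%: n = ln(0.05)/ln(0.99) = 298.07, so 299. The plan's 300 is reproduced. Registering 500 for 300 implies attrition of 1 − 300/500 = 40%. No sizing figure is given for chart 2.9.

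**Assumptions for chart 2.9, none stated in the documents**

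- A two-level factor, with patients split 250/250 or 450/50 (the 50 being the earlier-stopping level).
- The same constant first-reaction rate λ in both levels: 0.05, 0.1 or 0.2 per patient-year.
- Exponential stopping, unrelated to reactions, with proportion d stopped by year 3. The two values of d average 40%.
- Observation ends at last dose + 28 days or Day 1 + 1120, whichever is earlier. In 364-day years the lag is 28/364 = 0.0769, and (1120 − 28)/364 = 3.

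**Formulas.** With θ = −ln(1 − d)/3:

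- Mean observation = 0.0769 + d/θ
- Crude proportion p = 1 − e^(−0.0769λ) + λ·e^(−0.0769λ)·[1 − e^(−3(λ+θ))]/(λ+θ)

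**Example, λ = 0.1**

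- d = 25%: θ = 0.0959, mean observation 2.68 years, p = 0.0077 + 0.1 × 0.9923 × 0.4444/0.1959 = 23.3%.
- d = 55%: θ = 0.2662, mean observation 2.14 years, p = 0.0077 + 0.1 × 0.9923 × 0.6666/0.3662 = 18.8%.

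The true rates are equal, yet the crude ratio is 0.81.

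**Probability that Fisher's two-sided test gives p < 0.05.** Found by summing the binomial probabilities of all significant tables. Simulation with 4,000 tables per setting, run at 250/250 for every row except 35% vs 45%, agrees to within one percentage point.

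| Stopped by year 3 | Mean years | Crude %, λ = 0.1 | 250/250: λ = 0.05, 0.1, 0.2 | 450/50: same λ |
|---|---|---|---|---|
| 40% vs 40% | 2.43, 2.43 | 21.2, 21.2 | about 4% each | about 4% each |
| 35% vs 45% | 2.51, 2.34 | 21.9, 20.4 | 4.4, 5.5, 7.2% | 4, 4, 6% |
| 30% vs 50% | 2.60, 2.24 | 22.6, 19.6 | 6.8, 10.6, 17.7% | 4, 5, 9% |
| 25% vs 55% | 2.68, 2.14 | 23.3, 18.8 | 11.0, 19.9, 36.1% | 5, 8, 16% |
| 20% vs 60% | 2.77, 2.04 | 23.9, 18.0 | 17.5, 33.4, 59.1% | 7, 11, 25% |

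**Masking.** Keep 25% vs 55% stopping, but give the early-stopping level a 25% higher rate (0.125 vs 0.1). Its crude proportion is 0.0096 + 0.125 × 0.9904 × 0.6907/0.3912 = 22.8%, against 23.3%. The excess disappears.

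**After correction.** With a constant rate, mean person-time to first reaction or end of observation is p/λ. First reactions per 100 patient-years are therefore equal in the two levels in every row.

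**Front-loaded risk.** If the rate is five times higher in the first 3 months, the crude test rejects in 6% to 44% over the same λ and gaps of 30/50 to 20/60. A simple person-year rate then over-corrects slightly (ratio 1.04 to 1.10). A log-rank or Cox comparison does not have this problem.

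**The case against.** The strongest reply is that the effect may be small. The documents do not say that any factor is tied to stopping. At 35% vs 45% the test is close to nominal, and many listed factors, such as renal disorder or past tuberculosis, are probably uncommon, which lowers the rejection rate further. This stands, and it is why the size is given as a range.

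Second, chart 2.9 does not itself end observation at discontinuation. SAP section 2 runs to Day 1 + 1120 for everyone, and SAP 10.2 admits events from outside the survey form. But nominal inclusion is not follow-up: under the Protocol a stopped patient leaves the survey, so later events are caught only incidentally.

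Third, the consequence is limited. Significance in 2.9 only triggers further descriptive tables. Hepatic, renal, paediatric, elderly and self-administration tables are made regardless, and the priority items already get person-year rates in chart 2.4.2. This bears on severity. It does not remove a directional bias, because none of those outputs gives person-time by factor.

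A reader might infer that the crude test would usually mislead. Mean exposures of 2.8 vs 1.5 years at λ = 0.1 do give 1 − e^(−0.28) = 24.4% vs 1 − e^(−0.15) = 13.9%, significant in 82% of surveys with 250 per level. Under exponential stopping, however, those means require about 18% vs 82% stopped by year 3 between levels of one factor. Nothing in the documents supports so large a gap.

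Prior anti-TNFα treatment is a doubtful example: the wording of chart 2.9 appears to leave patients with that history out of the test.

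**Conclusion.** The point holds. Chart 2.9 mixes reaction risk with time under observation, although the plan expects substantial discontinuation and already allows for unequal follow-up in other charts. Under equal true rates, significance ranges from about nominal (4-7% at 35% vs 45% stopping) to 18-59% at 20% vs 60%, with 250 per level and λ from 0.05 to 0.2. It is lower when one level is small. A 25% true excess in early stoppers can vanish.

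These sizes rest on assumed rates, stopping proportions and group sizes, and on stopping being unrelated to reactions. If reactions cause stopping, that is a separate mechanism.

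A reader might also infer that an early-stopping level could look harmful. Through exposure time alone it can only look protective; it is the longer-treated level that looks harmful. Factors classified during treatment (concomitant medication or therapy, SAP 10.1) have a further problem: longer exposure raises both the chance of being classed as having them and the chance of a reaction.

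The change should be made, but the 2.9 results are exploratory and no primary conclusion depends on them.

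**What to change.** - In chart 2.9, add for each factor level the number of patients with a first reaction per 100 patient-years, using person-time to first reaction or end of observation.
- Base the test that selects factors for 2.9.xx on time to first reaction: log-rank or Cox, with a trend version for ordered factors.
- Censor at last dose + 28 days for discontinued patients and at Day 1 + 1120 otherwise, as in charts 2.6 and 2.7.
- Count only events inside that window in the rate and the test, so that numerator and person-time match. SAP section 2 alone would count later events against time that is not in the denominator.
- Keep the crude percentage, including undated and later events, as description.
- Flag concomitant medication and therapy as descriptive only. They stay biased after this change.

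The cost is modest programming, since exposure (SAP 10.1) and days to onset (SAP 10.2) are already derived and no new data are needed. The downside is that undated events and events after last dose + 28 days drop out of the test. The number of patients affected should be shown beside it.

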Humira® for Subcutaneous Injection

Protocol for Special Investigation

(Long-term treatment for Crohn's Disease patients)

AbbVie GK

Protocol No. P13-170

1. Purpose of the investigation

This special investigation of Humira for Subcutaneous Injection will be conducted to obtain information on the safety (especially profile of malignant tumors and serious infections) and effectiveness in patients with Crohn's disease who are receiving Humira for a long period of time.

2. Target number of patients

(1) Target sample size

A total of 500 patients.

(2) Rationale

The incidence of malignant tumors in clinical studies in CD patients conducted in- and outside Japan prior to the approval of Humira for CD were 1.1% (1/90 patients) and 1.1% (16/1459 patients). Based on these incidences, we plan to investigate 300 patients to detect at least one case of malignant tumor at a probability of 95%, and register 500 patients, since a substantial number of patients will discontinue or withdraw from the investigation.

3. Patients to be investigated

Patients who meet the following criteria at baseline will be evaluated in the investigation:

- (1) Patients with Crohn's disease indicated for Humira treatment with the recommended dosage regimen.
- (2) Patients with no past- or present malignant tumors.
- (3) Patients who are not currently receiving Humira.

4. Number of participating institutions by department

The investigation will be conducted in about 100 eligible institutions.

5. Criteria of participating institutions and investigators

The investigation will be conducted by the institutions and physicians that satisfy the following criteria and have concluded agreements with AbbVie GK. for implementation of the investigation.

(1) Participating institutions

Institutions that satisfy the following criteria will participate in the investigation:

- 1) Institutions that have concluded or will conclude agreement with AbbVie GK. for implementing the all-case investigation of Humira in patients with Crohn's disease
- 2) Institutions where the effectiveness of Humira can be evaluated using Crohn's Disease Activity Index (CDAI) whenever possible.

(2) Participating investigators

Investigators that satisfy the following criteria will participate in the investigation:

- 1) Physicians who have participated in the all-case investigation of Humira in Crohn's disease ^{*1}

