Sex, age (year), body weight (kg), BMI (kg/m²), duration of illness (year), indication (registration form), allergy history, smoking history, with smoking history (details), self-administration, tuberculosis test status, hepatitis B virus test status (registration form), complication, complication: liver disorder, complication: renal disorder, complication: blood disorder, complication: respiratory disorder, complication: diabetes mellitus, complication: osteoporosis, complication: malignant tumour, medical history, medical history: tuberculosis, medical history: non-tuberculous mycobacteriosis, medical history: interstitial pneumonia, medical history: bronchitis bacterial, medical history: aplastic anaemia, medical history: pancytopenia, medical history: malignant tumour, prior medication for Crohn's disease, prior medication: anti-TNF α drug, prior medication: aminosalicylic acid drug, prior medication: corticosteroids, prior medication: immunosuppressant, prior medication: antibiotics, prior treatment for Crohn's disease, prior treatment: surgery, prior treatment: GCAP, prior treatment: enteral nutrition therapy, prior treatment: intravenous nutrition therapy, treatment history with anti-TNF α drug for Crohn's disease, with treatment history with anti-TNF α drug for Crohn's disease, concomitant medication, concomitant medication: aminosalicylic acid drug, concomitant medication: corticosteroids, concomitant medication: immunosuppressant, concomitant medication: antibiotics, concomitant therapy for Crohn's disease, concomitant therapy: surgery, concomitant therapy: GCAP, concomitant therapy: enteral nutrition therapy, concomitant therapy: intravenous nutrition therapy, site of disease: anus/perianal region, site of disease: rectum, site of disease: stomach/duodenum, site of disease: colon, site of disease: jejunum/ileum, intestinal complication, non-intestinal complication, work condition, CDAI when the administration was started, CRP

"2.9.xx Incidence of adverse reactions per background factor and seriousness"

Patients for analysis: patients in the safety analysis group

Analysis objective: to show the onset status of non-serious/serious adverse reactions per statistically-significant background factor based on the test results in 2.9.

Analysis item: aggregate the following items per background factor and seriousness for adverse reactions which occurred in the safety analysis period.

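### For background factors without their own chart, the SOC/PT breakdown by seriousness depends on p<0.05 in chart 2.9, a test that can often miss a doubled risk in a small group, and chart 2.9 gives no confidence interval

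*SAP*

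**What the plan says.** Chart 2.9 (SAP 13.2) is meant "to show the incidence of adverse reactions per patient background factor and analyze them". For each listed factor it gives the number of patients and the number and percentage with adverse reactions and with serious adverse reactions. It adds "the tests for adverse reactions": the "exact test for nominal-scale factors", and a Mann-Whitney test for ordinal ones. No separate test of serious reactions is named, and no risk difference, odds ratio or confidence interval is planned.

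SAP 9.6 sets the threshold: "In principle, the significant level is 5%, two-tailed". SAP 9.5 adds: "Multiplicity is not adjusted".

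Chart 2.9.xx then shows non-serious and serious reactions by SOC and PT "per statistically-significant background factor based on the test results in 2.9".

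Five groupings have charts that do not depend on a test: self-administration (2.5.1, SOC/PT without the seriousness split), hepatic disorder (2.13.1), renal impairment (2.14.1), paediatrics (2.15.1) and the elderly (2.16.1).

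**The concern.** The factor list in chart 2.9 includes conditions that bear directly on the survey's focus, serious infection and malignancy. Examples are a history of tuberculosis, non-tuberculous mycobacteriosis or interstitial pneumonia, blood or respiratory disorder, diabetes, and concomitant corticosteroid or immunosuppressant. Several of these groups may be small. For them the type of reaction is tabulated only if a test of any reaction at all is significant.

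Such a condition favours large groups, where a modest difference reaches p<0.05, over small ones, where even a doubled risk may not. It also asks a different question from the one the table answers: an excess of infections in a risk group need not show in the any-reaction rate. Without an interval in chart 2.9, the reader of a non-significant result cannot see how large a difference remains compatible with the data.

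**Working it through.** **The plan's only sample-size figure.** About 300 evaluable patients are to give a 95% chance of at least one malignancy at roughly 1.0% (Protocol section 2, SAP 4.3). 1 − (1 − 0.01)^300 = 0.951, and ln 0.05 / ln 0.99 = 298.1, so n = 299. The figure reproduces. The registration target is "A total of 500 patients". No power is stated for chart 2.9.

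**Inputs for the check.**
- From the documents: two-sided 5%, Fisher's exact test for nominal factors, N = 300 or 500.
- Assumed, because the documents do not give them: exposed group size n1, reaction rate p0 in the unexposed, and a risk ratio of 2.

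**Method.** For x reactions among n1 exposed and y among N − n1 unexposed, sum Bin(x; n1, 2·p0) × Bin(y; N − n1, p0) over all tables with two-sided Fisher p<0.05. One minus that sum is the probability of missing the doubled risk.

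Miss probability, N = 300 (N = 500 in brackets):

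| n1 | p0 = 10% | p0 = 20% | p0 = 30% |
|---|---|---|---|
| 10 | 85% (85%) | 68% (66%) | 56% (56%) |
| 15 | 79% (77%) | 61% (60%) | 36% (35%) |
| 25 | 69% (66%) | 43% (41%) | 16% (15%) |
| 50 | 53% (51%) | 19% (16%) | 3% (2%) |
| 100 | 38% (28%) | 6% (2%) | <1% (<1%) |

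**Reading the table.** For n1 of 15 to 25 and p0 of 10 to 20%, the miss runs from 41% to 79%. Over n1 of 5 to 25 and p0 of 5 to 40%, it runs from about 2% (n1 = 25, p0 = 40%) to 94% (n1 = 5, p0 = 10%, N = 500). With 50 or more exposed and p0 of 20% or more, the test is adequate for a doubled risk. For a 1.5-fold risk (20% to 30%) with 60 of 300 exposed, the miss is 65%.

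**What the missing interval hides.** Take 4 of 10 exposed against 58 of 290 unexposed, which is 40% against 20%. Fisher p = 0.13; sample odds ratio = (4/6)/(58/232) = 2.7; exact 95% CI 0.5 to 11.6. Under the plan this factor would show two percentages and p = 0.13, and no 2.9.xx table. The interval would show that an eleven-fold odds ratio is not excluded.

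**The other direction.** The list has 61 entries. If all were tested at exactly 5% and none had an effect, about 61 × 0.05 = 3 would qualify by chance. That is an upper guide, since Fisher's test is conservative and not every entry is tested.

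**Other outputs.** Protocol section 9 and SAP 5.1 plan stratified analysis of malignancy, tuberculosis and serious infections. The priority-item charts 2.4.1.1, 2.4.1.2 and 2.4.2 are not split by background factor. For a factor without its own chart, 2.9.xx is therefore the only summary table in SAP chapter 13 that crosses type of reaction with the factor.

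**The case against.** A reader might infer that a non-significant result removes small risk groups from the safety report. It does not. Chart 2.9 shows every factor with its overall and serious incidence whatever the p-value, so the crude difference can be read off. Only the SOC/PT detail by seriousness is conditional.

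A reader might also infer that the plan treats non-significance as evidence of no effect. No passage says so. The SAP simply has no rule on how to report such a factor.

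The 40 to 80% could be taken as a property of the plan. It is not: it follows from assumed group sizes and rates, applies to Fisher's test only, and falls to a few per cent for larger groups or higher rates.

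Further points in the plan's favour:
- Chart 2.3 lists each patient's complications beside the adverse reactions, so for blood disorder, respiratory disorder or diabetes the cases can be traced one by one. It lists neither medical history nor seriousness, so the history factors gain nothing from it.
- Where the miss rate is highest, the lost table is thin. With 6 exposed at 40%, about 6 × 0.4 = 2.4 patients would have a reaction.
- Limiting descriptive follow-up tables by p-value is a common way to contain output in an uncontrolled survey, and the documents rest no treatment or labelling decision on 2.9.xx.

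These points narrow the concern and lower its weight. They leave standing the p-value condition, the absent interval and the lack of a tabulation by reaction type for the factors closest to the survey's stated focus.

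**Conclusion.** The point holds in a limited form. For background factors without their own chart, the SOC/PT breakdown by seriousness is produced only after p<0.05 on any adverse reaction, and the incidences that remain in chart 2.9 carry no confidence interval. With 15 to 25 exposed patients, a 10 to 20% reference rate and a true risk ratio of 2 (all assumed), Fisher's test misses the difference in about 40 to 80% of cases. Other assumptions give about 2% to over 90%. The calculation does not cover the ordinal factors. This is a cheap improvement to the reporting, not a flaw that undermines the survey's safety conclusions.

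**What to change.** 1. In chart 2.9, add for each nominal factor the risk difference or odds ratio with an exact 95% CI. State that a non-significant factor is reported as not shown to differ, with its upper limit.
2. Produce 2.9.xx whatever the p-value for a named list drawn from the existing factors:
   - medical history of tuberculosis, non-tuberculous mycobacteriosis, interstitial pneumonia, bacterial bronchitis, aplastic anaemia and pancytopenia;
   - complication of blood disorder, respiratory disorder and diabetes mellitus;
   - concomitant corticosteroids and concomitant immunosuppressant.

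   Keep the p<0.05 rule for the other factors.

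A threshold on the estimate should not replace the p-value for the listed factors. For example, requiring an odds ratio above 1.5 with a CI reaching 2 or more is still a noisy, data-driven filter. At an assumed 20% baseline with no true effect it would select 34%, 24% and 18% of factors with 6, 15 and 30 of 300 exposed. With a doubled risk it would still drop 24%, 17% and 9%.

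The data are already collected, and charts 2.13.1 to 2.16.1 already follow this practice for four groups. The cost is SAP wording, the estimate and interval in chart 2.9, and up to 11 further descriptive tables, some with few patients.
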